7.3 LOST TO FOLLOW-UP

N/A

8 STUDY ASSESSMENTS AND PROCEDURES

8.1 ENDPOINT AND OTHER NON-SAFETY ASSESSMENTS

Mixed methods of data collection will be used including audit of the electronic medical record (EMR) to extract routinely collected and previously recorded data, surveys, and field notes. The study team will follow the same measurement procedures for both study groups.

The primary and secondary outcomes (vaccine initiation and completion by age 13, respectively) will be assessed by audit of the EMR, completed by the research assistant (RA) and/or a member of the study team. To assess variation among providers in the same practice, we will sample records from each participating provider. Measurement will be completed over four 12-month time periods (baseline, 12, 24, and 36 months). For each measurement period, the physician's office will provide an electronic list of eligible patients with an office visit with each participating provider. For each practice, a member of the study team will randomly select a sample of 60 records per provider from this list for review by the RA and or other member of the study team. As much as possible the number of records will be balanced across providers. Data abstracted from the record will include date and type of index visit (well child, acute care, and other e.g., immunization), date of birth, date of vaccination for HPV vaccine, Tdap, and MCV, sex, race/ethnicity and insurance status. Records will be de-identified for patient, provider and practice identifiers, and given a unique subject ID number.

Providers: At baseline and at 12- and 24-months, in addition to the EMR audit described above, all participating providers will complete a brief survey to assess their knowledge, attitudes and behaviors regarding HPV vaccination. The baseline survey will also assess demographic and other practices and physician-level factors that may affect intervention success and are needed to describe the study sample. The practice facilitator will keep detailed field notes about practice observations, contextual factors and practice change components, and will monitor the implementation process.

Practices: At baseline, the project coordinator and/or a member of the study team will meet with the practice manager to complete a brief practice survey to describe the practice and current HPV vaccination procedures. HPV vaccination procedures will be reassessed in a similar manner at 12- and 24- months.

Following the conclusion of the intervention, intervention practices will be invited to participate in an exit interview with the PI to assess the providers and their staff's experiences in participating in the HPV vaccine intervention, and to get input from participants about potential improvements in the intervention. These interviews will be audio recorded, consent for recording will be verbal.

8.3 Adverse Events and Serious Adverse Events

8.3.1 DEFINITION OF ADVERSE EVENTS

The care being provided to patients by participating study practices is indicated and therefore the only potential adverse event is breach of confidentiality. Regular monitoring will occur and any breach of confidentiality will be reported to the IRB as required per institutional guidelines if necessary.

8.4 UNANTICIPATED PROBLEMS

8.4.1 DEFINITION OF UNANTICIPATED PROBLEMS

This protocol uses the definition of Unanticipated Problems as defined by the Office for Human Research Protections (OHRP). OHRP considers unanticipated problems involving risks to participants or others to include, in general, any incident, experience, or outcome that meets all the following criteria:

- Unexpected in terms of nature, severity, or frequency given (a) the research procedures that are described in the study-related documents, such as the IRB-approved research protocol; and (b) the characteristics of the subject population being studied.
- Related or possibly related to participation in the research.
- Suggests that the research places participants or others at a greater risk of harm (including physical, psychological, economic, or social harm) than was previously known or recognized.

8.4.2 UNANTICIPATED PROBLEMS REPORTING

The PI will report unanticipated problems to WU IRB as required per institutional guidelines if necessary.

9 STATISTICAL CONSIDERATIONS

9.1 STATISTICAL HYPOTHESES

- Primary Efficacy Endpoint(s):

We hypothesize that the 2-year intervention will increase the percentage of preteens who receive HPV vaccine before their 13th birthday by at least 13 percentage points at 24 months compared to control, and benefits will be sustained at 36 months.

Alternatively, our null hypothesis is that there will be no difference in HPV vaccine use between the intervention and control groups.

9.2 SAMPLE SIZE DETERMINATIONS

AIM 1: We will use a cluster randomized design. Study outcomes will be measured at the level of the patient using a cross-sectional design. The sample size determination is based on the primary outcome - initiation of HPV vaccination by age 13. Effectiveness is derived from the difference in the proportion of eligible preteens in the intervention and control groups 24 months after the intervention, and long-term maintenance is derived from the difference in these measures 36 months after intervention. In the control group, national data suggest the baseline vaccine initiation proportion should be 0.4. We expect the vaccine initiation proportion in the control group in this age group will not change over time, and intervention group will have a similar baseline initiation rate to the control group, but will increase by at least 0.13 by 24 months. Thus, the hypothesis to test is $H_0: p=0.4$ vs. $H_1: p=0.53$.

Our study has a three level hierarchical structure: children are clustered within providers which are clustered within practices. Thus, there exists correlations for children seen by the same provider, as well as providers working in the same practice. We use random effects to capture the intra-class correlation at the provider and the practice levels. From our preliminary data, the estimate for random effect variance at the practice level is very close to 0, and that at the provider level is 0.75² (corresponding to an ICC of 0.15). This suggests very little heterogeneity at the practice level, but significant heterogeneity at the provider level. Since there is no ready-to-use software for power calculation for clustered trial in the three level hierarchical structure, we conduct the power calculation by simulation.

In the simulation study, we set $\sigma_a^2 = .01$ for the random effect at the practice level and $\sigma_b^2 = .75^2$ for the random effect at the provider level. We choose the value of β so that the proportion of HPV vaccine rate is 0.4 for control and 0.53 for the intervention. We assume there are 4 physicians in each practice, each physician sees 30 children, resulting a total of 120 patients in each practice. The sample size to calculate is the number of practices. The simulation study is carried out in R, using function *glmer()* in the *mle4* package for estimation of the generalized linear mixed effects model (1) below.

Our original simulation results showed that 10 practices in the control arm and 10 practices in the intervention arm (a total of 120*20=2,400 children) would achieve a power over 0.80, to reject the null hypothesis under the significance level of 0.05. To address variation in the number of providers/practice, and to account for inclusion of more providers than anticipated (95 vs 80), we have chosen to increase

the sample size to 60 patients/provider, to ensure adequate power to detect a meaningful difference between the control group and the intervention group.

We also considered different baseline initiation rates in the control group in the range of 0.4 to 0.6. Our sample size of 10 practices in each arm has sufficient power to detect a difference in the rate of 0.12 when the baseline rate is 0.5 (i.e., $H_0: p = 0.5$ vs. $H_1: p = 0.62$), and 0.12 when the baseline rate is 0.6 (i.e., $H_0: p = 0.6$ vs. $H_1: p = 0.72$). In summary, the sample size of 20 practices provides adequate power to detect a 13% or larger effect.

To date, the literature suggests increased vaccination in 13-17 year-olds, but little year-to-year variation in vaccine outcomes in 11-12 year-olds, and so we have assumed no change in control group outcomes for our calculations. Finally, we considered the unlikely event of a 5% increase in vaccine initiation in the target group. In this case, our calculations suggest that a sample of 10/group would provide over 80% power to detect an 18% increase in the intervention group.

AIM 2: The joint significance test⁷⁹ will be used to test if the mediation effect is significant. The p-value from the joint significance test is the maximum of the p-values in testing $\alpha_1=0$ and $\gamma=0$ separately, that is, it requires that both α_1 and γ are significant simultaneously. We thus use a Bonferroni's correction to set the significance level to be $0.05/2=0.025$ for each test. We expect the power in testing $\gamma=0$ is lower since the outcome is a binary variable, while the mediator is a continuous or categorical variable which can yield more efficiency and higher power. Thus, we will repeat our simulation study in Aim 1 for power calculation, but use the alpha level of 0.025 instead of 0.05. Our sample size of 10 practices in each arm has sufficient power to detect a difference in the rate of 0.14 when the baseline rate is 0.4, and 0.13 when the baseline rate is 0.5 or 0.6. In summary, the sample size of 20 practices provides adequate power to detect a 14% or larger effect.

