For ~15-months, a practice facilitator has worked with 6 practices (20 providers) to implement the intervention, first targeting initiation of HPV vaccine by age 13. All practices were provided with their baseline data and received education about the potential benefit for patients and the practice for following CDC recommendations, a communication strategy, and patient education materials. They identified a QI team and worked with the facilitator towards the practice's goals for improvement. Each practice completed Plan-Do-Study-Act (PDSA) cycles, testing different strategies to improve care. PDSA cycles are small cycles of change that involve reviewing data to assess gaps in performance, identifying possible changes to improve care, selecting and testing an improvement strategy, and monitoring and adjusting new processes for care delivery. To date, the number of team meetings with the facilitator varied from 7 to 11, 10% were by phone, and each visit lasted < 1 hour.

For each provider, HPV initiation was assessed on a randomly selected sample of ~30 patients, 11.0 to 13.0 years old with at least one practice visit (well-child or acute care visit) between June 1st and September 30th in the measurement period. These included 2016, 2017, and 2018. Overall, there was a 19-percentage point increase in HPV vaccine initiation in the 15- months from pre- to post-intervention (62% to 81%), reaching the target for Healthy People 2020.³ Results varied within and across practices as shown in Figure 2.

Efforts to impact vaccine completion by age 13 were initiated in March 2018, and after only 7 months, we observed a 12% increase. The majority (>80%) of providers felt the following features of the intervention were very important in the change process: access to the practice facilitator, the QI practice team, help with measurement and review of vaccination data, and the communication strategy, and all would strongly recommend the program to their colleagues

These findings suggest that the proposed 2-year intervention is feasible and likely to have a large impact and sustained benefits.

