4 STUDY DESIGN

4.1 OVERALL DESIGN

We will complete a single site, cluster-randomized trial to evaluate the effectiveness of a multi-component implementation strategy (the intervention) to increase use of the HPV vaccine according to CDC guidelines. Randomization will occur after baseline assessment and the unit of randomization is a community-based, primary care pediatric practice. The randomization schema will be generated and implemented by the study statistician. Twenty practices will be randomized into two groups, the 2-year intervention group (n=10) or a wait-list control group (n=10). The intervention includes: 1) an educational video to increase the provider's knowledge about guideline recommendations and patient and practice benefits of vaccination by age 13; 2) audit and feedback of vaccine coverage to increase motivation to engage in practice change; 3) a communication strategy to improve the provider's communication skills and their self-efficacy to address parental hesitation; and 4) practice facilitation to support practice change to develop a sustainable HPV vaccine delivery system. The intervention will be delivered through a series of brief practice visits with the facilitator that occur every 1-4 weeks over 2 years. Vaccine use will be assessed at the practice level using 12-months of routinely collected clinical data to allow for seasonal variation in care delivery patterns. Vaccine use will be assessed at baseline, at 12 and 24 months to assess effectiveness, and at 36 months to assess if change is sustained. Due to the 2020 pandemic and overall concerns for safety, we will use ZOOM video conferencing for research activities, including obtaining measures and implantation of the intervention

The study hypotheses are: 1) *The 2-year intervention will increase the percentage of preteens who receive HPV vaccine before their 13th birthday by at least 13 percentage points, and benefits will be sustained at 36 months.* 2) *The intervention will increase on-time HPV vaccination by increasing providers' capability (communication skills) and their motivation (confidence in their capabilities) to deliver on-time HPV vaccination.*

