9.4 STATISTICAL ANALYSES

9.4.1 GENERAL APPROACH

All main data analyses will adhere to the intention-to-treat principle, and a probability of $P < 0.05$ will be used to establish statistical significance (2-tailed test). Before we perform complicated statistical modeling, we will conduct exploratory data analysis. For continuous variables, we will examine their distribution, and summarize them with mean/standard deviation if data are reasonably normally

distributed, or with median/interquartile range if data are skewed. We will use Rosner's outlier detection routine. Categorical data will be summarized by proportions. Simple comparison of continuous variables between intervention and control group will be performed using two sample t test or non-parametric Wilcoxon test. Simple comparison of categorical variable will be performed using chi-square test or fisher exact test where appropriate.

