9.4.2 ANALYSIS OF THE PRIMARY ENDPOINT(S)

Data analyses will adhere to the intention-to-treat principle, allowing 12-months grace period to implement practice changes. The primary analysis will compare the overall proportion of eligible preteens who initiated and completed HPV vaccination in the intervention and control practices at 24 months, using Year 2 measurements for vaccine use. Maintenance of change will be assessed using Year 3 measurements. The analytic approach is to use a multi-level random effects logistic model to account for the hierarchical structure: children clustered within providers clustered within practices.

Define by y_{ijk} as the binary variable of HPV vaccine for the k th child of provider j of practice i . There are 3 hierarchical levels: children clustered within providers clustered within practices. We use random effects to capture the intra-class correlation at the provider and the practice levels. We assume a multi-level random effects logistic model (a generalized linear mixed model):

$$\text{logit } P(y_{ijk}=1) = \beta_0 + trt_{ijk}\beta_1 + a_i + b_{ij} \quad (1)$$

[figure not shown]
where trt_{ijk} is the treatment indicator for practice i , and β_1 is the treatment effect. We use random effects a_i and b_{ij} to describe heterogeneity in the practice level and provider level, and assume $a_i \sim N(0, \sigma_a^2)$ and $b_{ij} \sim N(0, \sigma_b^2)$ are independent. The practice level random intercept is used to accommodate extra-variation in outcome measurements due to clustering of providers in a practice, and the provider level random intercept is used to accommodate extra-variation in outcome measurements due to clustering of individual patients within a provider.

As secondary analysis, we can add other covariates in the model, e.g., gender, category of practice (urban vs. rural), vaccine rate at baseline for a provider or practice, etc. Interaction of treatment and these covariates can be included in the model to study the moderating effect of these risk factors. The interaction of random effects (both at the practice and provider levels) and covariates can be added in the model as well.

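### With 20 practices randomised, the primary test of the treatment effect has no stated statistic, degrees of freedom or small-sample method; the default Wald z would over-reject if practices differ more than assumed

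*Combined protocol and SAP*

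**What the plan says.** Section 4.1 randomises 20 practices, 10 to each arm. Section 6.3 stratifies them by number of providers (up to 4, or 5 and more) and uses blocks within strata, without giving block sizes.

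For the primary endpoint, section 9.4.2 states: "The analytic approach is to use a multi-level random effects logistic model to account for the hierarchical structure". Model (1) has a treatment indicator and random intercepts for practice and provider. Section 9.4.1 sets two-sided significance at 0.05. Neither section says how the treatment coefficient is tested: there is no statistic, reference distribution, degrees of freedom, small-sample correction, permutation test or practice-level analysis.

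Software for fitting model (1) appears only in section 9.2, for the power calculation: "The simulation study is carried out in R, using function" glmer. There, "we set $\sigma_a^2 = .01$ for the random effect at the practice level and $\sigma_b^2 = .75^2$ for the random effect at the provider level". The reason given for the small practice variance is that in preliminary data "the estimate for random effect variance at the practice level is very close to 0". The dataset is not named. No type I error check and no power run at another practice variance is reported.

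**The concern.** Treatment varies only between practices, so the information about its standard error comes from 20 units. A Wald z treats the estimated practice variance as known, and maximum likelihood tends to underestimate that variance with so few practices. When practice variance is truly near zero this matters little, because provider variation dominates and there are many more providers. When it is not near zero, the standard error is too small on average, and both the primary p-value and the confidence interval are too optimistic.

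Section 6.1.1 places the intervention at practice level and section 6.1.2 tailors its schedule to each practice, so practices could differ more at 24 months than at baseline. Leaving the test open also allows it to be chosen after the data are seen.

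**Working it through.** **Inputs from the documents**
- 20 practices, 10 per arm (4.1); two-sided 0.05 (9.4.1).
- Initiation 0.40 against 0.53; practice variance 0.01; provider variance 0.75² = 0.5625; 4 providers per practice and 30 children per provider (9.2). This is 80 × 30.
- Current design: 95 providers and 60 records each (9.2), in practices of 2 to 8 providers (10.4). This is 95 × 60.

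**Assumptions, not in the documents**
- Larger practice variances of 0.1, 0.2 and 0.3 on the logit scale.
- The split of the 95 providers over the 20 practices.
- Use of glmer and its default test in the analysis.

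**Method.** Data were generated from model (1), with intercepts solved so that the marginal rate, averaged over both random effects, equals the target. Each trial was fitted with glmer. The Wald z was compared with 1.96 and also with the t critical value on 18 df (20 practices − 2 arms). An unweighted two-sample t-test on the 20 practice proportions was run alongside. The Monte Carlo SE is √[p(1−p)/N]; for p = 0.074 and N = 2,500 it is √(0.074 × 0.926/2,500) = 0.005.

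**1. The plan's own figure.** At 80 × 30, practice variance 0.01, and 0.40 against 0.53, Wald z power is 0.873 (1,000 runs). The stated power of over 0.80 is reproduced.

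**2. Type I error, nominal 5%** (1,500 to 2,500 runs per row)

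| Design | Practice variance | Wald z | Mixed model, t on 18 df | Practice-level t-test |
|---|---|---|---|---|
| 80 × 30 | 0.01 | 5.0% | 3.6% | 4.7% |
| 80 × 30 | 0.1 | 7.4% | 5.9% | 5.5% |
| 80 × 30 | 0.2 | 7.8% | 6.0% | 5.2% |
| 80 × 30 | 0.3 | 8.0% | 6.4% | 5.3% |
| 95 × 60 | 0.01 | 5.4% | 3.7% | 4.7% |
| 95 × 60 | 0.1 | 8.5% | 6.8% | 5.5% |
| 95 × 60 | 0.2 | 8.5% | 6.6% | 5.6% |

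A second set of glmer simulations (1,500 runs each) gave:
- 95 × 60 at 0.01, 0.1 and 0.2: Wald z 4.7%, 8.6% and 8.8%; t on 18 df 4.0%, 6.7% and 6.9%.
- 80 × 30 at 0.01 and 0.1: Wald z 6.1% and 6.7%.

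A smaller 80 × 30 run (1,000 each) gave Wald z 4.1%, 5.6% and 7.5% at 0.01, 0.1 and 0.2.

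**3. Permutation test.** Re-randomising practices within the two size strata (95 × 60, assumed split) gave 4.6% to 5.1% at variances from 0.01 to 0.2.

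**4. How firm is a near-zero estimate?** Section 2.2 describes two earlier datasets: 6 practices with 20 providers, and 10 practices with 16 providers. Take either, as an assumption, with 30 children per provider at a rate of 0.4, and use a balanced ANOVA approximation.
- Variance of a provider's logit about the practice mean: w = 0.5625 + 1/(30 × 0.4 × 0.6) = 0.701.
- With a practices and n providers each, the maximum-likelihood practice variance is exactly zero when an F variable is below [a/(a−1)]/(1 + n × variance/w).
- 6 practices (n = 3.33), true variance 0.1: 1.2/1.475 = 0.81; on 5 and 14 df the probability is 44%. At 0.2: 1.2/1.951 = 0.62, probability 31%.
- 10 practices (n = 1.6): 43% at 0.1 and 34% at 0.2.

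A zero estimate would therefore be common even if the true variance were large enough to cause over-rejection.

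**The case against.** The strongest reply is that the plan has not been shown to use the test that misbehaves. glmer is named only for the power simulation, and section 9.4.2 is silent on software. That stands. A reader might infer that the planned primary test has an error rate near 9%. The documents do not support this: the Wald z is an inferred default, and values close to 9% come only from the top of the range in the 95 × 60 design with an assumed split of providers.

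Second, at the plan's own variance of 0.01 there is no inflation; the runs centre on 5%. That also stands. The excess needs a practice variance at least ten times larger, and no such value is in the documents.

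Third, the pilot remark "Results varied within and across practices" (section 2.2) might be read as evidence of practice-level variance. It is not. With practice variance zero, about 3.33 providers per practice and 30 records each, practice logits would have variance 0.701/3.33 = 0.21. That is an SD of 0.46, or about 0.46 × 0.24 = 0.11 on the probability scale. Visible spread across practices is expected under the plan's assumption. The 4- to 5-fold spread among providers within a practice (section 2.2) also fits heterogeneity at provider level.

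Fourth, it is tempting to say the 0.01 rests on the six pilot practices. Section 9.2 does not say so; that source is possible, not stated.

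What remains is the omission itself, and an assumption that earlier datasets of the size described could not firmly establish.

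**Conclusion.** The concern holds in a conditional form. The plan tests a practice-level treatment with 20 practices and leaves the test and its reference distribution unspecified. If the glmer default were used, type I error would be about 5% at practice variance 0.01. At 0.1 to 0.3 it would be about 7% to 8.5% in most simulations, with two 80 × 30 runs at 0.1 lower (5.6% and 6.7%). The inflation rests on the assumed variance range, the inferred default test and, for the current design, the assumed split of providers. The documents show neither that the variance is that large nor that the primary result will be wrong. They also contain no safeguard if it is, and one is cheap to add.

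**What to change.** In section 9.4.2, name the primary test of the treatment effect and take the confidence interval from the same method. Either of these would serve:
- a permutation test that re-randomises practices according to the actual blocks within the two provider-number strata, with the permuted statistic named and the block sizes recorded, and an interval by test inversion; or
- an unweighted t-test on the 20 practice proportions with 18 df and its interval. This targets the difference in mean practice proportions, not the conditional log odds ratio of model (1), and the text should say so.

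The mixed model can still be reported as a supporting estimate. Do not rely on t with 18 df applied to its coefficient as the correction: it still rejects 6.6% to 6.9% in the 95 × 60 design at variances of 0.1 and 0.2.

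The change needs some wording and a little programming, and no new data. At the plan's inputs, 80 × 30 power falls from 0.873 (Wald z) to 0.838 (practice-level t-test). For 95 × 60, power with these tests is about 0.86 to 0.89. Both stay above 0.80. If practice variance is really 0.1 to 0.2, power is about 0.6 to 0.7 with these tests. The choice of test is not the main cause: Wald z itself reaches only 0.62 at 0.2 in the 80 × 30 design. Section 9.2 should report power over a range of practice variances.

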9.4.3 ANALYSIS OF THE SECONDARY ENDPOINT(S)

We will use mediation analysis to test whether the provider's capability and provider's beliefs about their capabilities mediate the intervention's effect on vaccination outcomes.

Define the provider's beliefs about their capabilities by M_{ij} , we can write the model as

$$M_{ij} = \alpha_0 + trt_{ijk}\alpha_1 + c_i + e_{ij} \quad (2)$$

$$\text{logit } P(y_{ijk}=1) = \beta_0 + trt_{ijk}\beta_1 + M_{ij}\gamma + a_i + b_{ij} \quad (3)$$

We are interested in testing the hypothesis $H_0: \alpha_1\gamma = 0$ vs. $H_1: \alpha_1\gamma \neq 0$. The joint significance test⁷⁹ can be used to test the significance of the mediation effect. We include random effect c_i to capture the correlation of the provider's capabilities within the same practice. The indirect effect, i.e., the effect of intervention to the outcome through the mediator is specified as the product of α_1 and γ . The direct effect of treatment on outcome is denoted by β_1 . We can use a similar model for provider's capability.

Finally, we can also include the interaction of treatment and mediator in Model (3), to test whether the mediator is also a moderator of treatment in the "mediator moderator" model.

We will use mediation analysis to test whether the intervention effect on vaccination outcomes is mediated by the degree of practice change as measured by an 18-item HPV vaccine delivery score.

For implementation outcomes (fidelity, acceptability, appropriateness), we will complete a descriptive analysis. Parental satisfaction will be modeled in a three-level (practice, provider, and child's parent) linear mixed effects model. Descriptive statistics will be given on implementation fidelity, the acceptability and appropriateness of the intervention for providers, parental satisfaction with care, and cost. Of note, fidelity score is measured at the practice level every 6 months in the intervention group only. Parental satisfaction is measured in both study groups at baseline and 24 months. Provider acceptance and appropriateness is measured in intervention group at 24 months.

Denote by y_{it} the fidelity score of practice i at time t . Repeated measures of fidelity score will be modeled by mixed effects models.

$$y_{it} = \beta_0 + \beta_1 t + a_i + e_{ij}, \quad (4)$$

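### Aim 2 halves alpha for a both-paths mediation test that needs no correction, quotes total-effect power as mediation power, and leaves collected baseline measures out of the non-randomised path

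*Combined protocol and SAP*

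**What the plan says.** Section 9.2 (AIM 2) uses the joint significance test: "The p-value from the joint significance test is the maximum of the p-values" for the treatment-to-mediator path (α1) and the mediator-to-outcome path (γ), and both must be significant. From this it concludes "We thus use a Bonferroni's correction to set the significance level", that is, 0.05/2 = 0.025 per path.

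For power it argues that γ is the weaker path because the outcome is binary, "while the mediator is a continuous or categorical variable which can yield more efficiency and higher power". It therefore says "we will repeat our simulation study in Aim 1 for power calculation, but use the alpha level of 0.025 instead of 0.05". The result is a detectable difference in vaccination rate of 0.14 at a baseline rate of 0.4, and 0.13 at 0.5 or 0.6. The closing line reads "In summary, the sample size of 20 practices provides adequate power to detect a 14% or larger effect".

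Section 9.4.3 gives the models. It starts "Define the provider's beliefs about their capabilities by" M_ij, one value per provider. Model (2) regresses M_ij on treatment with a practice effect c_i, included "to capture the correlation of the provider's capabilities within the same practice". Model (3) regresses vaccination on treatment, M_ij and random effects, with no covariates. Section 8.1 states: "At baseline and at 12- and 24-months, in addition to the EMR audit described above, all participating providers will complete a brief survey". Vaccine coverage is also audited at baseline.

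Mediation is a secondary objective in Section 1.1 and tertiary/exploratory in Section 3. It is also the second of the two hypotheses in Section 4.1.

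**The concern.** There are three points of different standing.

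**(a) The alpha split does not follow from the rule (wrong as written, but conservative).** Bonferroni protects a claim that succeeds if *either* test succeeds. Here *both* must succeed. Halving alpha prevents no false claim that needed preventing, and it lowers the chance of detecting true mediation. Section 9.4.1 sets 0.05 for the main analyses and Section 9.4.3 gives no level for mediation, so the level that will be applied is also unclear.

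**(b) The power figure describes a different test (wrong as written).** Model (1) contains neither α1 nor γ. A reader is told that Aim 2 is adequately powered when no mediation power was computed, and could take a null mediation result as evidence against the mechanism.

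**(c) The γ path is open to confounding that collected data could reduce (an improvement, not a misstatement).** Randomisation protects α1 but not γ. Section 2.2 reports that low confidence distinguished providers with lower coverage. Stable provider traits would explain that as well as a causal effect would. If such traits drive both belief and coverage, any shift in belief can make the joint test positive although belief does not drive vaccination.

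**Working it through.** **Inputs from the documents.** Practice variance 0.01 and provider variance 0.75²; 10 practices per arm, 4 providers per practice, 30 children per provider (Section 9.2, AIM 1). The same section later gives 95 providers and 60 charts each. Practices have 2–8 providers (Section 10.4).

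**Assumed, because the documents give no values.** Mediator SD 1 and ICC 0.05; belief shifts of 0.3, 0.5 and 0.8 SD; a range of odds ratios per SD; test-retest correlation 0.6 for belief and 0.7 for coverage; belief–coverage correlation from stable traits of 0.10, or 0.25–0.42.

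**1. Reproducing the plan's figures.** Simulating model (1) with the plan's inputs (1,500 replicates, rates read as marginal proportions) gives this total-effect power at alpha 0.025:

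- 0.40 vs 0.54: 0.835
- 0.50 vs 0.63: 0.781
- 0.60 vs 0.73: 0.850

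These match the claim of sufficient power at about 0.80, so the Aim 2 figures are total-effect power at a smaller alpha.

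**2. Error of the both-paths rule.** If at least one path is null, P(both reject) ≤ P(the null path rejects) = alpha per path.

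- At 0.05 per path the cap is 0.05; with both paths null and independent it is 0.05² = 0.0025.
- At 0.025 per path the cap is 0.025; with both null it is 0.025² = 0.000625.
- Simulation with a 0.8 SD shift and γ = 0: joint rejection 5.1% at 0.05 and 2.5% at 0.025.
- Cost: if each path has 80% power at 0.05, joint power is 0.80² = 0.64. At 0.025 each path has 0.712, and 0.712² = 0.51.

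**3. Power of the joint test.** Provider-level simulation, 95 providers, 60 charts, 4,000 runs per case, total effect 0.40 vs 0.54 (0.638 on the logit scale). The mediated share is ln(OR) × shift / 0.638.

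| Belief shift | OR per SD | Mediated share | Joint power at 0.025 |
|---|---|---|---|
| 0.3 SD | 1.70 | 0.531 × 0.3 / 0.638 = 25% | 0.19 |
| 0.5 SD | 1.38 | 0.322 × 0.5 / 0.638 = 25% | 0.47 |
| 0.8 SD | 1.22 | 0.199 × 0.8 / 0.638 = 25% | 0.51 |
| 0.8 SD | 1.49 | 0.399 × 0.8 / 0.638 = 50% | 0.88 |

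Total-effect power at 0.025 was 0.88–0.91 in every scenario, while joint power over all scenarios ran from 0.10 to 0.89. With 80 providers and 30 charts the ranges were 0.79–0.82 and 0.08–0.85. The 0.025 level cost 5–13 points of joint power; at 0.5 SD and OR 1.38, power was 0.58 at 0.05 and 0.47 at 0.025. Full mixed models on that case (600 runs) gave 0.56 and 0.45.

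**4. Is γ the weaker path?** The shift detectable on α1 alone with 80% power at 0.025 is (2.24 + 0.84) × √(1/W1 + 1/W0), where W is the sum over an arm's practices of m/(1 + (m − 1) × ICC). For 10 practices of 4 per arm:

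- ICC 0: W = 40, giving 3.08 × √(2/40) = 0.69 SD
- ICC 0.05: W = 40/1.15 = 34.8, giving 0.74 SD
- ICC 0.10: W = 40/1.30 = 30.8, giving 0.79 SD

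With 95 providers the values are 0.63, 0.70 and 0.75 SD. At smaller shifts α1 can be the limiting path. In a separate simulation with 80 providers, 30 charts and a 0.5 SD shift, power at 0.05 was 0.51 for α1 and at least 0.94 for γ.

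**5. The non-randomised path.** Here γ = 0 and belief and coverage are correlated 0.25–0.42 through stable traits only. Entries are the rates at which mediation is falsely declared.

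| Belief shift | Plan: 0.025, no baseline terms | Baseline-adjusted, 0.05 per path |
|---|---|---|
| 0.3 SD | 9–17% | 4–9% |
| 0.5 SD | 26–46% | 8–17% |
| 0.8 SD | 48–84% | 9–21% |

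At a correlation of 0.10 the plan's rate is 1–10%. With only 30 baseline charts per provider the adjusted ranges are 5–11%, 9–20% and 12–25%. At 0.5 SD and OR 1.38, adjustment with 0.05 per path raises power from 0.47 to 0.81.

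**The case against.** The facts in (a) and (b) are hard to dispute. The case on the other side concerns the remedy and the weight.

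- **Keep 0.025 and adjust.** In a rerun of the confounding set-up, adjustment at 0.025 gave false-mediation rates of 1.5–3%, 5–8% and 6–12% for the three shifts, roughly half those at 0.05. Adjustment alone brought power at 0.5 SD and OR 1.38 to 0.71, so most of the rise from 0.47 to 0.81 comes from the baseline terms. This stands as a reading of where the gain arises. It does not justify the split: a smaller alpha always lowers false positives, but it does not treat confounding.
- **Multiplicity.** Aim 2 has two provider mediators, an exploratory practice-change score and two vaccination outcomes, and the 0.05 cap holds for one mediator–outcome pair only. That is true, but it is not the reason given, and the plan already ranks the provider mediators as primary and secondary. If multiplicity is the purpose, the SAP should say so and define the family.
- **Assumed values.** The correlations of 0.25–0.42 are not in the documents; Section 2.2 reports interviews with 16 providers. At a correlation of 0.10 and 0.5 SD, adjustment at 0.05 gave 5.9% against the plan's 4.6%, which is no gain. The power of 0.81 falls to 0.69 with test-retest values of 0.4 and 0.5, and to 0.65 with 0.3 and 0.5. Section 8.1 also does not name the belief item in the baseline survey. These limits stand for the sizes in (c).
- **Low-end scenarios.** Some cases had as little as 10% of the effect mediated, where low power is expected. Yet with the share fixed at 25%, joint power still ran from 0.19 to 0.51.

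**Conclusion.** The concern holds. The 0.025 level does not follow from the rule that is said to require it; the error is conservative. The adequate-power statement for a 14-point effect is power for the total effect and says nothing about α1 × γ. Neither conclusion depends on any assumed value. The sizes do: joint power between 0.10 and 0.89 beside total-effect power of 0.88–0.91, and false mediation of 26–46% at a 0.5 SD shift with correlations of 0.25–0.42. Repeating the main cases with 1,000 runs each gave similar values: joint power 0.17 (0.3 SD, OR 1.70), 0.43 (0.5 SD, OR 1.38) and 0.89 (0.8 SD, OR 1.49), and false mediation of 25–47% falling to 7–14% with baseline terms and 0.05 per path. The baseline terms are a worthwhile improvement rather than the correction of an error. The primary analysis and the trial size are unaffected. The SAP should be corrected because mediation is one of the two stated hypotheses.

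**What to change.** 1. In Section 9.2 (AIM 2), delete the Bonferroni sentence, and in Section 9.4.3 state that each path is tested at two-sided 0.05. Make this change together with item 3, because relaxing alpha alone would raise the false-mediation rate.
2. Replace the 14% sentence with simulated power of the joint test under models (2) and (3), including c_i. State the assumed belief shift in SD units, the odds ratio per SD and the mediator ICC, and use the current provider and chart numbers.
3. Add the baseline mediator and the provider's baseline coverage to model (3). Add the baseline mediator to model (2) for precision only.
4. Because false mediation can stay above 5% after adjustment, describe a positive result as consistent with mediation, not as proof of it.

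The cost is SAP wording and one simulation; no new data are needed. The restated power will look less favourable than the present sentence unless the belief shift is large.
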